9.2 Withdrawal Period Efficacy Analysis

9.2.1 Handling of Missing Data

Missing data will be handled as described below for the Withdrawal Period efficacy analysis.

9.2.1.1 Time-to-Flare

After handling of intercurrent events, for subjects without observed flare event, time-to-flare will be censored at the last available flare assessment at or prior to Week 152 visit.

9.2.1.2 Binary Endpoints

Non-responder Imputation (NRI) will be used, in which all missing data after handling of intercurrent events will be categorized as non-responders.

9.2.1.3 Continuous Endpoints

After handling of intercurrent events, Mixed -Effect Model Repeat Measurement (MMRM) will be used as the primary approach for handling missing data.

Mixed-Effect Model Repeat Measurement (MMRM)

MMRM will be utilized in the analysis of continuous endpoints (refer to Section 9.2.2). The MMRM analysis will be conducted based on observed data, and includes the categorical fixed effect of visit and the continuous fixed covariates of Original Baseline measurement. For summary of the overall subjects, an additional fixed effect of parent study (Study 1 or Study 2) will be considered. An unstructured variance covariance matrix will be used. The MMRM analysis is based on the assumption of data being missing at random (MAR).

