For the purposes of baseline characteristics, efficacy analysis and safety analysis, Original Baseline is defined as the value last observed prior to the first administration of study drug in the parent study, Study 1 or Study 2. The Original Baseline is used as the baseline value for all change or percent change from baseline efficacy analyses in the Withdrawal Period and for all safety summaries. For the purposes of efficacy analysis, Re-treatment Baseline is defined as the baseline value of the Re-treatment Period, which is the value last observed prior to the first administration of re-treatment study drug in the Remission-Withdrawal Period. The Re-treatment Baseline is used as the baseline value for all change or percent change from baseline efficacy analyses in the Re-treatment Period.

All analyses and summary will be performed and presented for overall (all eligible subjects) and by indication for Study 1 (bDMARD-IR AS) and Study 2 (nr-axSpA) subgroups (eligible subjects enrolled in Study 1 and Study 2, respectively).

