9.2.2 Efficacy Analyses in the Withdrawal Period

The distribution of event-free survival defined in Section 3.1 will be estimated using Kaplan-Meier (KM) method. Subjects who did not have flare event will be censored at the last available flare assessment visit at or prior to Week 152 visit. If a subject discontinued prior to flare or Week 152 visit, the data will be censored at the date of last flare assessment. The KM estimator for median survival time for the flare-free rate during the Withdrawal period will be provided. The corresponding 95% CI will be derived based on Greenwood's formula for variance derivation and the log-log transformation applied on the survival function. The KM plot will be provided.

Binary and continuous endpoints defined in Section 3.1 and Section 3.2 will be analyzed at scheduled time points during the Withdrawal Period.

For binary endpoints, NRI will be used for missing data handling (see Section 9.2.1.2). Descriptive statistics, including point estimate and 95% CI by normal approximation, will be provided.

For continuous endpoints, MMRM model (as described in Section 9.2.1.3) will be used based on observed data. Mean estimates with associated 95% CI will be provided. In addition, descriptive statistics based on observed data will be provided, including the number of observations, mean, and standard deviation.

Plots of efficacy endpoints by visit during the Withdrawal Period will be provided for selected endpoints.

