9.3.1.2 Continuous Endpoints

Mixed-Effect Model Repeat Measurement (MMRM) analysis based on all observed data will be conducted with categorical fixed effect of visit and Re-treatment Baseline as the continuous fixed covariate. For summary in the overall subjects, an additional fixed effect of parent study (Study 1 or Study 2) will be considered. An unstructured variance covariance matrix will be used.

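### The single-group MMRM adjusts for baseline, so its usual 95% CI omits the sampling variation of mean baseline and is generally too narrow for the population mean change

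*SAP*

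**What the plan says.** The withdrawal efficacy analysis has a single group, subjects off upadacitinib (SAP 4.0, Table 1). SAP 2.2 fixes the reference value: "The Original Baseline is used as the baseline value for all change or percent change from baseline efficacy analyses in the Withdrawal Period". SAP 9.2.1.3 gives the model for continuous endpoints, which "includes the categorical fixed effect of visit and the continuous fixed covariates of Original Baseline measurement". It adds "An unstructured variance covariance matrix will be used" and, for the pooled summary, "an additional fixed effect of parent study (Study 1 or Study 2) will be considered". There is no baseline-by-visit term.

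SAP 9.2.2 then says "Mean estimates with associated 95% CI will be provided" and, in addition, "descriptive statistics based on observed data will be provided, including the number of observations, mean, and standard deviation". SAP 9.3.1.2 uses the same form after flare, "with categorical fixed effect of visit and Re-treatment Baseline as the continuous fixed covariate", and 9.3.2 reports means with 95% CIs and the same observed-data summary.

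The SAP does not say at which baseline value the model mean is evaluated, whether the interval is conditional on baseline, or whether its target is the mean change in the population of remitters or the mean change at the observed mean baseline. No hypothesis is tested (SAP 9.1 and 13.0).

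**The concern.** In a randomised comparison, baseline adjustment sharpens the treatment contrast, and the uncertainty in mean baseline largely drops out because both arms share it. Here there is no contrast: the reported quantity is the mean change itself, and that includes the sample mean of baseline. A standard error that holds this mean fixed leaves out a real source of sampling variation.

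The objective in SAP 2.1 concerns maintenance of disease control in subjects who reached remission. That is naturally a statement about a population, not about one set of baseline values. A reader will take the interval as uncertainty about the mean change in such patients. No other interval planned for mean change would correct that reading.

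**Working it through.** **Inputs.** The model terms come from SAP 9.2.1.3 and 9.3.1.2. Neither document gives a sample size, SD, correlation or CI width for this period, so there is no stated figure to reproduce. All SDs, correlations and sample sizes below are assumptions.

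**Formulas.** Let SDx be the baseline SD, SDy the SD at the visit, r their correlation and n the number of subjects.

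- Slope of change on baseline: b = r·SDy/SDx − 1.
- Model variance of the mean at the sample-mean baseline: SDy²(1 − r²)/n.
- Sampling variance of the mean change: (SDy² + SDx² − 2·r·SDx·SDy)/n.
- Difference, which is what the model interval omits: (r·SDy − SDx)²/n = b²·SDx²/n.
- SE ratio = √(model variance / sampling variance); coverage = 2Φ(1.96 × SE ratio) − 1.

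**ASDAS-type inputs (assumed).** The variance columns are multiplied by n.

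| SDx | SDy | r | b | Model | Omitted | Total | SE ratio | Coverage |
|---|---|---|---|---|---|---|---|---|
| 0.8 | 0.6 | 0.2 | −0.85 | 0.346 | 0.462 | 0.808 | 0.65 | 80% |
| 0.8 | 0.8 | 0.2 | −0.80 | 0.614 | 0.410 | 1.024 | 0.77 | 87% |
| 0.8 | 0.8 | 0.4 | −0.60 | 0.538 | 0.230 | 0.768 | 0.84 | 90% |
| 0.7 | 0.9 | 0.3 | −0.61 | 0.737 | 0.185 | 0.922 | 0.89 | 92% |
| 0.8 | 0.4 | 0.2 | −0.90 | 0.154 | 0.518 | 0.672 | 0.48 | 65% |

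The last row is the case where the visit SD is only half the baseline SD. For scale, take the first row with an assumed n = 60. The model half-width is 1.96·√(0.3456/60) = 0.15 ASDAS units, against 1.96·√(0.808/60) = 0.23 for the population mean change.

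**Range.**

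- SDy = SDx: coverage is 83.4% at r = 0, 88.6% at 0.3, 91.0% at 0.5, 92.9% at 0.7 and 94.4% at 0.9.
- SDy = 0.75·SDx: coverage is 76-86% over r = 0 to 0.9.
- SDy = 1.25·SDx and r = 0.8: b = 0, the SE ratio is 1.00 and coverage is 95%.

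**Check on the stated model.** The MMRM (common baseline slope, unstructured covariance) was simulated with assumed n = 60, four visits and 300 replicates per setting, both with complete data and with data removed after a flare-like value. Monte Carlo error is about 1 to 2 percentage points.

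| Slope of follow-up score on baseline | Coverage |
|---|---|
| 0.2 at all visits | 85-87% |
| 0.5 at all visits | 86-92% |
| Rising from 0.1 to 0.5 over visits | 82-88% |
| 0.95 (score tracks baseline closely) | 92-95% |

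A contrived case, with complete data and a slope of change that is zero only at the last visit, gave 97.3% at that visit. The single common slope inflates the residual variance there.

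**Where ASDAS is likely to sit.** Entry requires ASDAS < 1.3 at Week 104 and < 2.1 at Week 88. In a group held to a narrow low range two years after Original Baseline, early off-drug scores probably depend little on that baseline, which puts b near −1. This is an inference, not a figure from the documents.

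**The case against.** The strongest reply is that the SAP never states the construction criticised here. It promises only mean estimates with an interval. If the target is mean change at the observed mean baseline, the conditional interval is valid. That stands as a statement about wording, but the SAP does not name that target, and its objective points to a population.

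Second, the observed n, mean and SD are also planned. If they are given for change, a reader can form SD/√n. At early withdrawal visits, when few subjects have been re-treated, this is close to the unconditional SE. In the Re-treatment Period, all collected data are used regardless of discontinuation (SAP 8.0), so the workaround is better still. Later in withdrawal it weakens: values after re-treatment are excluded and only the MMRM implicitly imputes them, so the two summaries drift apart. In either period no interval is planned for the observed mean.

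Third, nothing is tested, and the Kaplan-Meier and binary-endpoint intervals are unaffected. This limits the consequence, not the error.

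Three stronger readings are tempting, and the documents do not support them:

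- **Every continuous endpoint is affected.** The shortfall vanishes at b = 0, is small for scores that track baseline, and can reverse at a visit under a common slope. Nothing in the documents fixes b for BASMI, MASES, joint counts or ASAS HI.
- **The near −1 slope carries over to re-treatment.** Re-treatment Baseline is taken around flare, so the Week 104 remission argument does not transfer.
- **The pooled mean is mis-weighted.** The parent-study effect is only to be considered, and equal weighting is a software default the SAP does not state. With an assumed 30/70 split and study means 0.3-0.5 apart, equal weights would shift the mean by (0.5 − 0.3) × 0.3 to 0.5 = 0.06-0.10 ASDAS units. Results are also shown by study. This is missing detail, not a demonstrated error.

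**Conclusion.** The concern holds in limited form. If the planned intervals are built in the usual way, they omit b²·SDx²/n and are generally too narrow for the population mean change when change depends on baseline. On assumed inputs, coverage is about 80-92% for ASDAS-type scores after withdrawal, and about 65% if the visit SD is half the baseline SD. It is near nominal for scores that track baseline closely. The algebra applies equally to the Re-treatment Period, but the size there is not quantified.

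The conclusion rests on two readings the SAP leaves open: the default model interval, and a population target. The sizes rest on SDs and correlations that the documents do not supply. No test or decision rule depends on these intervals, so the effect is on how precise the descriptive results appear.

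**What to change.** In SAP 9.2.1.3 and 9.3.1.2, state that the interval's target is the population mean change from the relevant baseline, and use an unconditional variance by one of three routes:

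- Put baseline into the response vector as visit 0, with visit as the fixed effect and unstructured covariance, and report the visit-minus-baseline contrast with its CI.
- Keep the current model and add b²·SDx²/n to the squared SE. This is simplest, but it is exact only if one slope fits all visits.
- Bootstrap subjects.

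The cost is SAP wording, a few lines of code and wider intervals. The widening factor is 1/(SE ratio): ×1.53, ×1.29, ×1.20 and ×1.12 for the first four rows of the ASDAS-type table. For the visit-0 route with six scheduled withdrawal visits, the unstructured covariance grows from 6·7/2 = 21 to 7·8/2 = 28 parameters. The SAP should therefore name a fallback in case the model does not converge in a small subgroup.

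As a secondary clarification, if parent study stays in the overall model, specify observed-margin weights so that the pooled mean describes the subjects actually analysed.

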Long-term efficacy analysis will be performed similarly as described above, corresponding to the composite estimand for binary endpoints and the treatment policy estimand for continuous endpoints. For binary endpoints, supplementary analysis using the treatment policy estimand may also be conducted on all data as observed. For efficacy analysis beyond the placebo-controlled period (Week 14 in Study 1 [bDMARD-IR] and Week 52 in Study 2 [nr-axSpA]), no statistical comparison will be performed; descriptive statistics and 95% CIs will be provided. The analyses will be performed by randomized treatment sequence as described below:

1. Placebo → upadacitinib 15 mg QD
2. Upadacitinib 15 mg QD → upadacitinib 15 mg QD

Efficacy Analysis for the Remission-Withdrawal Period

For time to flare during the withdrawal period, the Kaplan-Meier (KM) curve will be provided based on as observed data. Subjects who discontinue the Remission-Withdrawal Period (prior to observed flare) will be considered censored. Subjects who receive retreatment will be considered flared. The KM estimator and associated 95% CIs for the flare-free rate during the withdrawal period will be provided. Similar analyses will also be performed for time to flare between Week 52 and Week 104 for Study 1 and Study 2 as well as for M16-098 (SELECT-AXIS 1).

For analysis of binary endpoints at scheduled visits during the withdrawal period, non-responder imputation will be used, where subjects who flare, discontinue the study, or have missing values are considered non-responders. For analysis of continuous endpoints, MMRM will be used. For all endpoints, analysis based on as observed data will also be performed. Descriptive statistics and 95% CIs will be provided. Data after retreatment will be excluded from these analyses and analyzed separately.

For subjects who receive re-treatment of upadacitinib after disease flare, analysis of endpoints after re-treatment will be based on data as observed. Change from baseline and improvement response are calculated from the retreatment baseline. Descriptive statistics and 95% CIs will be provided.

Subgroup Analysis for Efficacy

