2.2 Study Design Overview

Figure 1 shows the design of Study M19-944. Remission-Withdrawal Period is illustrated in the right portion.

Figure 1. Study Schematic

AS ankylosing spondylitis; ASAS Assessment of Spondyloarthritis International Society; bDMARD IR biologic disease modifying antirheumatic drug inadequate responder; EMA European Medicines Agency; FDA Food and Drug Administration; MRI magnetic resonance imaging; nr axSpA non radiographic axial spondyloarthritis; QD once daily; SI sacroiliac; UPA upadacitinib

Subjects in Study M19-944 from both Study 1 (AS bDMARD-IR) and Study 2 (nr-axSpA) who reach Week 104 on study drug (upadacitinib 15 mg QD) will be assessed whether they are in remission, with an ASDAS (CRP) < 1.3 at Week 104 and an ASDAS (CRP) < 2.1 at Week 88.

Subjects in remission at Week 104 will be eligible for the Remission-Withdrawal Period. Subjects will be followed without study drug treatment and assessed for disease flare through Week 152. Flare is defined as an ASDAS (CRP) \geq 2.1 at 2 consecutive visits (based on observed records), which are at least 2 weeks apart, or an ASDAS (CRP) > 3.5 at one visit. Subjects who flare will receive open-label re-treatment upadacitinib

15 mg QD from the time of flare for 24 weeks (re-treatment) or longer per local country requirements. Subjects who do not flare will be followed without upadacitinib treatment until Week 152 at which point they will have the option to receive open label upadacitinib for the predefined time period, if Week 152 is before the end of the Open-Label Extension Period for their respective country. If Week 152 is after the end of the Open-Label Extension Period, the subject will complete the study at Week 152.

Efficacy analyses will be performed to characterize subject response to treatment withdrawal up to 48 weeks and response to upadacitinib re-treatment for 24 weeks respectively. Safety analyses will be performed to assess safety of reinitiated upadacitinib 15 mg QD after treatment withdrawal, including re-treatment after flare and treatment during Open-Label Extension Period after withdrawal.

An additional safety analysis will be performed to assess the totality of upadacitinib safety in the M19-944 study.

For the purposes of subject disposition and efficacy analysis, the duration of withdrawal from treatment is defined as the Withdrawal Period. The 24 weeks of exposure to treatment after flare is defined as the Re-treatment Period.

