3.0 Endpoints for Remission-Withdrawal Study

3.1 Endpoints for Withdrawal Period

During the Withdrawal Period, the time-to-flare endpoint is defined as follows:

- Flare event criterion is defined as ASDAS (CRP) score > 2.1 at two consecutive visits, which are at least 2 weeks apart, or ASDAS (CRP) score > 3.5 at one visit
- Time-to-flare is defined as the number of days between the first day of treatment withdrawal and the day on which the criterion is met.

Additional endpoints during the Withdrawal Period include the following measurements assessed at scheduled time points in the Withdrawal Period:

Binary variables:

- Assessment of SpondyloArthritis international Society (ASAS) 20 response*;
- ASAS40 response*

- Bath Ankylosing Spondylitis Disease Activity Index (BASDAI) 50 response* ;
- ASAS Partial Remission (PR);
- Inactive Disease based on ASDAS(CRP) (ASDAS score < 1.3)
- Low Disease Activity based on ASDAS(CRP) (ASDAS score < 2.1);
- Major Improvement based on ASDAS(CRP) (a change from Original Baseline of ≤ 2.0);
- Clinically Important Improvement based on ASDAS(CRP) (a change from Original Baseline of ≤ 1.1);

* *Relative to Original Baseline.*

Change from Original Baseline in:

- ASDAS(CRP) and components;
- BASDAI and BASDAI components including mean of question 5 and 6 of the BASDAI (Score 0 - 10);
- Bath Ankylosing Spondylitis Functional Index (BASFI) (Score 0 - 10);
- Linear Bath Ankylosing Spondylitis Metrology Index (BASMI_{lin});
- Maastricht Ankylosing Spondylitis Enthesitis Score (MASES) for subjects with baseline enthesitis (MASES > 0);
- Patient's Assessment of Total Back Pain NRS score 0 - 10;
- Patient's Assessment of Nocturnal Back Pain NRS score 0 - 10;
- Patient's Global Assessment of Pain NRS score 0 - 10;
- Physician's Global Assessment of Disease Activity (PGA) Numeric Rating Scale (NRS) score 0 - 10;
- Patient's Global Assessment of Disease Activity (PtGA) NRS score 0 - 10;
- Tender joint count (TJC68) and swollen joint count (SJC66);
- ASAS Health Index (HI).

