8.0 Handling of Potential Intercurrent Events

For the Withdrawal Period, the potential intercurrent event is upadacitinib re-treatment. The following strategies will be used to handle the intercurrent event in efficacy analysis:

- For time-to-flare endpoint, the composite strategy will be used. Subjects who receive upadacitinib re-treatment without meeting disease flare criterion will be considered flared at the time of first dose.
- For binary endpoints, the composite strategy will be used to handle intercurrent events. Subjects who receive upadacitinib re-treatment will be considered as non-responder for all Withdrawal Period visits after first dose date.
- For continuous endpoints, the hypothetical strategy will be used to handle intercurrent events. All data after first dose date of upadacitinib re-treatment will be excluded from analysis and will be implicitly imputed by the statistical model.

For the Re-treatment Period, the potential intercurrent event is premature discontinuation of re-treatment study drug. The following strategy will be used to handle the intercurrent event in efficacy analysis:

- For all endpoints, the treatment-policy strategy will be used to handle intercurrent events. All collected efficacy data will be used as observed, regardless of whether the subject discontinued re-treatment study drug prior to the completion of the Re-treatment Period.

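### Withdrawal-period MMRMs for the non-ASDAS continuous endpoints leave out the ASDAS history that decides which data are removed, so MAR generally fails and off-drug worsening is likely understated

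*SAP*

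**What the plan says.** SAP 8.0 sets the handling of re-treatment in the Withdrawal Period: "For continuous endpoints, the hypothetical strategy will be used to handle intercurrent events", and "All data after first dose date of upadacitinib re-treatment will be excluded from analysis and will be implicitly imputed by the statistical model". Protocol 7.3 names MMRM for these endpoints and agrees on the exclusion: "Data after retreatment will be excluded from these analyses and analyzed separately".

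The trigger is in SAP 2.2: "Subjects who flare will receive open-label re-treatment upadacitinib", with flare set at an ASDAS (CRP) at or above "2.1 at 2 consecutive visits (based on observed records), which are at least 2 weeks apart, or an ASDAS (CRP) > 3.5 at one visit".

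The model is in SAP 9.2.1.3. It "includes the categorical fixed effect of visit and the continuous fixed covariates of Original Baseline measurement", with an unstructured covariance across visits and, for the overall summary only, a parent-study effect. For all continuous endpoints alike, "The MMRM analysis is based on the assumption of data being missing at random (MAR". Neither ASDAS nor flare status enters the model for any other endpoint. SAP 9.2.2 adds only observed-data descriptives. No joint model, auxiliary variable, multiple imputation or departure-from-MAR analysis is planned. SAP 9.1 and 13.0 make the period descriptive, without testing.

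**The concern.** An MMRM recovers excluded values correctly if, given the data inside that model, exclusion carries no further information about them. For ASDAS this is nearly so, because the values that decide exclusion are the model's own. For BASFI, BASMI, MASES, back pain, PGA, TJC/SJC or ASAS HI, the deciding variable is outside the model. A flared subject's later off-drug course is projected from subjects with a similar history on that endpoint who stayed off drug, that is, from subjects whose ASDAS remained lower.

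The objective (SAP 2.1) is maintenance of disease control after withdrawal. The subjects whose off-drug values are filled in are those who lost control. If the filled-in values are too favourable, the plotted and tabulated visit means make withdrawal look milder than it is.

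**Working it through.** The plan states no sample size, power, flare rate or correlation for this period, so there is no figure of its own to reproduce.

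**1. The condition.** Let Y be the endpoint, A be ASDAS, and H_Y, H_A their histories before visit j. Exclusion at visit j is a function of H_A. The own-history model fills in E[Y_j | H_Y, still off drug], whereas the target for an excluded subject is E[Y_j | H_Y, flared]. The two agree if Y_j is independent of H_A given H_Y. The SAP neither states nor justifies this.

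**2. Where it holds.** It holds if the endpoint is unrelated to ASDAS, if endpoint and ASDAS share the same correlation pattern over time (separable covariance), or if the endpoint is a Markov process that ASDAS merely reads with noise. Elsewhere it generally fails.

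**3. Simulation inputs.** From the documents: ASDAS < 1.3 at Week 104; visits at Weeks 110, 116, 122, 128, 140 and 152 (Protocol Appendix D); flare at ASDAS ≥ 2.1 at two consecutive visits or > 3.5 once; values after the flare visit removed and the flare visit kept. The Week 88 condition was not imposed. Assumed: ASDAS and the endpoint share a latent random-slope process (loading 0 to 1), ASDAS visit noise has SD 0.35, and endpoint noise has SD 0.2 to 1.0. Each setting generated 300,000-400,000 subjects before the Week 104 selection. The SAP model was fitted as maximum likelihood for monotone missing data: sequential regression on Original Baseline and own earlier visits. Starting the history at Week 104 or Week 110 made no material difference.

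**4. Results.** Mean worsening from Week 104 to Week 152; error = (estimate − true) / true, computed before rounding.

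| Flaring | Loading / noise SD | True | Own history | Error | With ASDAS history |
|---|---|---|---|---|---|
| 35.8% | 0 / 0.5 | 1.301 | 1.301 | 0.0% | 1.302 (0.0%) |
| 35.8% | 0.5 / 0.5 | 1.303 | 1.265 | −2.9% | 1.304 (+0.1%) |
| 35.7% | 0.7 / 1.0 | 1.300 | 1.181 | −9.2% | 1.306 (+0.5%) |
| 35.8% | 1 / 0.7 | 1.301 | 1.168 | −10.2% | 1.315 (+1.1%) |
| 35.8% | 1 / 1.0 | 1.304 | 1.116 | −14.4% | 1.317 (+1.0%) |
| 17.2% | 1 / 1.0 | 0.599 | 0.519 | −13.4% | 0.612 (+2.1%) |
| 58.4% | 1 / 1.0 | 1.996 | 1.639 | −17.9% | 2.013 (+0.8%) |
| 80.8% | 1 / 1.0 | 2.800 | 2.147 | −23.3% | 2.802 (+0.1%) |

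Worked example, fifth row: (1.116 − 1.304) / 1.304 = −14.4%.

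**5. Cross-checks.** ASDAS on its own history gave a Week 152 mean of 2.161 against a true 2.166, essentially unbiased. The Markov case gave a Week 152 mean of 1.936 against 1.937, and a separable-covariance run gave zero bias. One setting reversed the sign, to about +0.7%: an endpoint less noisy than ASDAS, with error correlation 0.8. Observed-data descriptives do not rescue the estimate: in the fifth row they gave 0.983 against 1.304, an error of (0.983 − 1.304) / 1.304 = −24.6%.

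**6. Small samples (also assumed).** With a shared slope and 23% flaring, the own-history model understated worsening by 2-11% and adding ASDAS history brought the error to about 0%. At n = 50-200 the SD of the estimate rose by about 2-7%, and the root mean squared error was within about 3% of the own-history model's or better.

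**The case against.** The strongest reply is that the period's question is already answered without this bias. SAP 8.0 uses a composite strategy for time to flare and for the binary endpoints, so re-treated subjects count as flared or as non-responders, and the ASDAS model is nearly unbiased. What remains is a set of additional endpoints with no decision rule attached. This stands, and it limits the priority of the point. A reader might infer that the period's conclusion on disease control is biased as a whole; the documents do not support that.

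A reader might also infer that worsening is necessarily understated, or that a fixed upper bound can be put on the bias. Neither follows. The direction needs a positive residual link between ASDAS history and the endpoint's future, which is expected but not shown, and the size moves with the assumed flare rate, link and noise.

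Three more points stand in part. Values up to the flare visit stay in the model, and PtGA and some BASDAI items are ASDAS components (SAP 7.1, Table 3), so some endpoints already carry part of the trigger. Gaussian simulations represent MASES and joint counts poorly. The bias can also be modest beside sampling error: at 30% flaring and n = 40-120 it was 0.04-0.13 points against a sampling SD of 0.11-0.29. With a moderate link at n = 40-70, root mean squared error was about the same with or without ASDAS history (for example 0.204 without against 0.209 with). That argues against expecting a large gain in accuracy, but not against removing a systematic error at little cost.

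That the SAP follows the protocol's MMRM and exclusion rule is true, but it does not make the MAR statement hold.

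**Conclusion.** The point holds in a conditional form. For continuous endpoints other than ASDAS, MAR given own history generally fails, because exclusion is decided by a variable outside the model. Where ASDAS history adds information, the off-drug worsening after Week 104 is likely understated: by about 0% with no link, separable covariance or a Markov endpoint; by up to roughly 10-15% at about 20-40% flaring; and by up to about 23% at very high flare rates. All these figures rest on the assumed shared-slope model.

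The percentages refer to worsening from Week 104. The SAP reports change from Original Baseline (section 2.2), so the absolute error carries over but the percentage does not. In the fifth row of the table the absolute error is 1.304 − 1.116 = 0.188 simulated units.

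Time to flare, the binary endpoints and the ASDAS model are not materially affected. The ASDAS model is not exactly MAR either, since SAP 8.0 allows for re-treatment without a qualifying flare and ASDAS can be calculated at unscheduled visits. No error rate is involved. The change is worth making before the final analysis, but it is not critical.

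**What to change.** Amend SAP 9.2.1.3 for each continuous endpoint other than ASDAS. Multiply impute the excluded off-drug values from the endpoint's own history plus the off-drug ASDAS (CRP) history. Impute ASDAS forward in the same sequence, so that no on-drug value after re-treatment is used. Impute on the two studies pooled with parent study as a covariate, then estimate visit means overall and by study and combine them by Rubin's method, which Protocol 7.3 already uses elsewhere. Report the own-history MMRM alongside, since the protocol names it, and reword the MAR sentence to say what each model conditions on.

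ASDAS is already calculated at every scheduled withdrawal visit (Protocol Appendix D), so no new data are needed. The cost is a SAP paragraph, modest programming and a standard error about 2-9% larger in simulation. A full bivariate unstructured model is not recommended for the by-study subgroups: with six visits it needs 12 × 13 / 2 = 78 covariance parameters, against 6 × 7 / 2 = 21.

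Separately, SAP 3.1 words the trigger as "Flare event criterion is defined as ASDAS (CRP) score > 2.1 at two consecutive visits, which are at least 2 weeks apart", whereas SAP 2.2 and the protocol include a value of exactly 2.1. These passages must be reconciled, because the imputation depends on who counts as flared.
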